## 7.4 Handling of Missing, Unused, and Spurious Data and Dropouts

Missing data are a potential source of bias when analyzing study data. A rigorous study design and execution will help prevent the incidence of missing data from occurring.

The primary analysis of the primary and secondary objectives will include subjects who follow DTM-LE programming and provide data (Per-protocol Analysis Set). Sensitivity analyses will be performed for the primary objective using Completer Analysis Set, as well as Implanted Analysis Set with the Multiple Imputation (MI) methodology for missing data.

## 7.5 Adjustments for Multiple Comparisons

As there is no hypothesis testing for the primary objective, adjustment for multiple endpoints is not required.

## 7.6 Demographic and Other Baseline Characteristics

Demographic and other baseline characteristics will be summarized for the Enrolled, Implanted, and/or Per-protocol Analysis Sets (section 7.1.3) as appropriate. Subjects with missing or unknown demographic data will be excluded from the relevant analysis, with a count of subjects with missing data provided. Listings of age at baseline, sex, race, and ethnicity will be included. A listing of activity goals at baseline will also be included.

## 7.7 Treatment Characteristics

Device exposure is summarized in section (7.10 Safety Evaluation).

The number and percent of patients who report at least a 50% improvement in pain at the Device Trial End Visit will be summarized.

Only medications used specifically for the treatment of back and/or leg pain will be collected during the study. Pain medications will be collected at baseline, and any changes to pain medications will be collected throughout the study. All pain medications will be coded using the appropriate version of the World Health Organization (WHO) Drug Dictionary at the appropriate Anatomical Therapeutic Chemical (ATC) level. Any changes to a subject's pain medications while they are enrolled in the study will be documented in the subject's medical records and the concomitant medications eCRF. The analysis of these concomitant medications is summarized in section 7.9.3.10.

## 7.8 Interim Analyses

No interim analyses are planned for this study.

## 7.9 Evaluation of Objectives

### 7.9.1 Primary Objective

The primary objective is to characterize changes in overall (back and leg) pain intensity, as measured by visual analog scale (VAS), from Baseline to 3-Month visit in subjects with devices programmed to DTM-LE SCS.

#### 7.9.1.1 Hypothesis

There is no hypothesis testing for the primary objective. The primary objective is to characterize the overall pain relief from baseline to 3-Month visit in subjects with DTM-LE SCS.

#### 7.9.1.2 Endpoint definition and derivation

Pain will be assessed using a VAS (0-10 cm) with 0 cm meaning "no pain" and 10 cm meaning "worst pain imaginable". Overall pain is defined as a combination of back and leg pain, but not pain from other body parts. Subjects will be asked to report their average pain intensity (overall, back, and leg) that is related to their SCS device treatment "in the last 24 hours" by marking a line perpendicular to the VAS line at the point that represents their pain intensity. Site personnel will determine the score by measuring the distance (cm) on the 10-cm line between the left, "no pain" anchor and where the subject's mark meets the line. The total length of the line will be measured (to ensure that it is 10 cm) and the distance from the "no pain" mark to the subject's mark divided by the total distance of the line will be recorded. The scored VAS ranges from 0 – 10. The overall pain intensity as measured by VAS will be collected at both baseline and 3-Month visit. The primary endpoint of change in overall pain VAS is

calculated using VAS at the 3-Month visit minus VAS at the baseline visit. A negative change is an improvement.

### **7.9.1.3 Analysis Methods**

The change in overall pain VAS as well as overall pain VAS at both baseline and the 3-Month visit will be summarized using descriptive statistics, (e.g., mean, standard deviations, etc.). The 95% CI of the mean change will be calculated.

In addition, percentage of change in overall pain VAS will be calculated for each patient using change in overall pain VAS divided by overall pain VAS at baseline. A negative percentage of change in VAS is a percentage of reduction in VAS, thus an improvement. The percentage of change in overall pain VAS will be summarized using descriptive statistics, (e.g., median and inter-quartile range, etc.)

### **7.9.1.4 Determination of Subjects/Data for Analysis, Sensitivity Analysis**

The primary analysis will use subjects who are implanted with Intellis neurostimulator, follow DTM-LE programming, and provide outcome measures at both baseline and 3-Month visit (Per-protocol Analysis Set).

Two sensitivity analyses will be performed. The first uses the Completers Analysis Set (7.1.3) who have outcome measures at both baseline and 3-Month visit and will be performed in the same way as the primary analysis method above. The other sensitivity analysis uses the Implanted Analysis Set (7.1.3) and will be performed using Multiple Imputation (MI) method for missing data at the 3-Month Visit. For scheduled 3-Month visit, if an Unscheduled Visit occurred within the 3-Month visit window, and the VAS is collected at the Unscheduled Visit, the VAS from the Unscheduled Visit will be used in the analysis of the 3-Month visit. Otherwise, the missing VAS will be imputed using MI. Prior to the use of MI, the distributions of the continuous variables will be assessed for normality and transformation may be considered if they are not normally distributed. The model variables in MI may include, but are not limited to study site, subject age, gender, primary diagnosis, VAS at baseline, 1-Month visit. The fully conditional specification method with 10 burn-in iterations within SAS and 10 repetitions (M = 10) will be used for imputation. Constraints will be set so that the imputed VAS are restricted to values ranging from 0-10. Following imputation, the objective will be evaluated using MI analysis method.

## **7.9.2 Secondary Objective**

To characterize programming parameters associated with energy use from Device Trial through 12-Month visit.

### **7.9.2.1 Hypothesis**

There is no hypothesis testing for the secondary objective. The secondary objective is to characterize programming parameters associated with energy use.

### **7.9.2.2 Endpoint Definition and derivation**

Subject's programmed settings (frequency, pulse width, and amplitude) together with the impedance range measurements and cycling ON-OFF time will be summarized.

### **7.9.2.3 Analysis Methods**

The programming parameters associated with energy use will be summarized using descriptive statistics, (e.g., mean, standard deviation, etc.) from Device Trial through 12-Month visit. Where possible, the energy use may be summarized by average recharge interval.

### **7.9.2.4 Determination of Subjects/Data for Analysis**

The analysis will use subjects who are implanted with the Intellis neurostimulator, follow DTM-LE programming, and have available data at Device Trial, 1-Month, 3-Month, 6-Month, or 12-Month visits (Per-protocol Analysis Set). One sensitivity analysis will be performed using the Completers Analysis Set, which will use subjects with available data at baseline and follow up visits of Device Trial, 1-Month, 3-Month, 6-Month, and 12-Month visits, respectively.

An overview of the additional objectives is given in Table 7-1Table 7-1.

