--	--

	
will be programmed to DTM-LE SCS settings. Programming parameters will be collected. Imaging will be collected, if performed.
 
Post-Implant Telephone Calls
 
Subjects will be called weekly by delegated study site personnel post-device activation to assess their pain relief status up to the 3-Month Visit and then monthly following the 3-Month Visit. If an in-clinic visit falls on the week or month of a scheduled telephone call, the call will not be performed. If the subject reports inadequate pain relief, they may be contacted by a sponsor representative (e.g., field clinical engineer) to assess for re-programming and/or come in for an unscheduled visit.
 
Post Implant 1-, 3-, 6-, and 12-Month/Final Study Visit (<math>\pm 15</math> days post Device Activation)
 
Post implant visits will occur at 1-, 3-, 6-, and 12-month post device activation. At the 1-month visit, stimulation threshold testing will be performed in the upright and supine positions for each programmed group. Imaging and programming parameters will be collected through the 12-Month/Final Study Visit, if re-programming or imaging occurs.
 
The following measures will be collected during follow-up:
 

• VAS (all follow-up visits)

• [REDACTED]

Safety Assessments	This study will collect and characterize all device-related, therapy-related, and procedure-related adverse events and device deficiencies from the Device Trial Start Visit until study exit.

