## 10.2 Data Collection

Study procedures, tasks and data collection requirements are summarized in [Table 10-1](#) below.

Table 10-1: Data collection and study procedure requirements at subject visits

Study Procedures, Tasks, and Data Collection (row) by Visit (column)	Enrollment/Baseline Visit	Device Trial Start Visit	Device Mid-Trial Visit e	Device Trial End Visit	Device Implant Visit	Device Activation Visit	1-, 3-, 6-, and 12-Month/Final Study Visit	Post-implant Phone Calls	Unscheduled Visits
Informed Consent Process	✓						✓		
Demographics	✓								
Inclusion/Exclusion Criteria	✓	✓		✓	✓				
VAS – overall, back, and leg	✓						✓		✓
Medical/Surgical History	✓								
Programming Parameters f		✓	✓ b	✓ b		✓	✓		✓ b
Imaging		✓			✓	✓ d	✓ d		✓ d
Device information (model, serial/lot number)		✓			✓				
Pain relief/programming feedback								✓	
Initial and final setting device interrogation report(s)		✓	✓ b	✓	✓	✓	✓		✓ b
AE/DD		✓	✓	✓	✓	✓	✓	✓	✓
Pain Medications	✓	✓	✓	✓	✓	✓	✓	✓	✓
b Perform activity only if unit reprogrammed									
d If acquired									
e Not a required study visit, only performed if necessary									
f May include electrode impedance measurements									

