## 10.12 Post-Implant Scheduled Visits

### 10.12.1 1-Month Visit

The 1-Month visit will occur 30 days  $\pm$  10 days after device activation (Day 0). Following the completion of all subject assessments required for this visit (see below), AdaptiveStim™ as well as the Position Diary will be turned ON and the device will be oriented. AdaptiveStim™ will then be turned OFF and stimulation threshold testing will be performed in the upright and supine positions for all programmed groups. AdaptiveStim™ may be turned back on, if needed, on an individual basis with sponsor approval. Before configuring AdaptiveStim™ Technology, it is recommended to allow a 4-week healing period after implanting the neurostimulator to allow time for the implanted components to stabilize. If there is not a  $\geq 50\%$  decrease in the VAS for overall pain collected at the visit compared to the Baseline VAS for overall pain, the subject may be re-programmed within the following limits:

Device interrogation report(s) with initial and final programmed settings will be uploaded via CDU. Imaging may be performed to assess for lead migration if deemed necessary by the investigator.

The following information will be collected during the 1-Month Follow-up visit:

- VAS
- [Redacted]
- Programming parameters/device interrogation report(s) with initial and final settings
- Imaging (if performed)
- Changes to pain medications
- AEs/DDs

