### 10.12.2 3-Month Visit

The 3-Month visit will occur 90 days  $\pm$  15 days after device activation (Day 0). If there is not a  $\geq 50\%$  decrease in the VAS for overall pain collected at the visit compared to the Baseline VAS for overall pain, the subject may be re-programmed. If re-programming occurs, device interrogation report(s) with initial

and final programmed settings will be uploaded via CDU. Imaging may be performed to assess for lead migration if deemed necessary by the investigator.

The following information will be collected during the 3-Month Follow-up visit:

- VAS
- [REDACTED]
- Programming parameters/device interrogation report(s) with initial and final settings
- Imaging (if performed)
- Changes to pain medications
- AEs/DDs

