### **10.12.3 6-Month Visit**

The 6-Month visit will occur 180 days  $\pm$  30 days after device activation (Day 0). If there is not a  $\geq$  50% decrease in the VAS for overall pain collected at the visit compared to the Baseline VAS for overall pain, the subject may be re-programmed. If re-programming occurs, device interrogation report(s) with initial and final programmed settings will be uploaded via CDU. Imaging may be performed to assess for lead migration if deemed necessary by the investigator.

The following information will be collected during the 6-Month Follow-up visit:

[figure not shown]
- VAS
- Programming parameters/device interrogation report(s) with initial and final settings
- Imaging (if performed)
- Changes to pain medications
- AEs/DDs

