### **10.14 Device Interrogation**

For visits occurring at the study site, device interrogation report(s) with initial and final interrogation settings as well as electrode impedance measurements must be obtained and uploaded via CDU when programming occurs, if applicable. Source for the interrogation reports should be kept at the study site. It is recommended that data are not cleared during any interrogation.

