### **10.17.11 Programming Parameters**

Programming parameters will be collected during the Device Trial, Device Implant, Device Activation, 1-, 3-, 6-, and 12-Month visits. Programming parameters will also be collected at unscheduled visits, as applicable. Imaging collected as a part of standard of care will also be collected during the study to be used in reference to programming.

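### For the 3- and 6-Month visits the protocol gives two rules for collecting device settings and impedance; the conditional rule would supply secondary-endpoint data mainly from poor responders

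*SAP*

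**What the plan says.** The secondary objective is to describe programming parameters linked to energy use from Device Trial to 12 months (SAP 4.2). SAP 7.9.2.2 lists the content: frequency, pulse width, amplitude, impedance range and cycling times. SAP 7.9.2.4 takes implanted subjects who "follow DTM-LE programming, and have available data at Device Trial, 1-Month, 3-Month, 6-Month, or 12-Month visits (Per-protocol Analysis Set"), with a Completers sensitivity analysis.

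Three places in the protocol require the settings at each scheduled follow-up visit:
- Section 10.17.11: "Programming parameters will be collected during the Device Trial, Device Implant, Device Activation, 1-, 3-, 6-, and 12-Month visits".
- Table 10-1: the follow-up column has plain ticks in both the programming-parameter row and the interrogation-report row. The footnote "Perform activity only if unit reprogrammed" is attached to some other visits but not to this column.
- The lists of information to be collected in 10.12.2 and 10.12.3, which carry no condition apart from imaging.

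Four places attach a condition:
- Synopsis, follow-up visits: "Imaging and programming parameters will be collected through the 12-Month/Final Study Visit, if re-programming or imaging occurs".
- Section 10.12.2 (3-Month): "If re-programming occurs, device interrogation report(s) with initial" and final settings are uploaded.
- Section 10.12.3 (6-Month): "If re-programming occurs, device interrogation report(s) with initial and final programmed settings will be uploaded via CDU".
- Section 10.14: initial and final settings "as well as electrode impedance measurements must be obtained and uploaded via CDU when programming occurs, if applicable".

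The 1-Month section, 10.12.1, states the upload without the condition: "Device interrogation report(s) with initial and final programmed settings will be uploaded via CDU".

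**The concern.** Sections 10.12.2 and 10.12.3 each contain both rules, so a site can follow the visit text in good faith and still not upload a report for a subject who was not re-programmed. Protocol 10.19.2 makes this matter: programming and device data are obtained through interrogation, moved to the site computer by CDU and stored from there in the sponsor's database for analysis. An upload that is not made is therefore a record missing from the secondary analysis.

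The loss would not be random. At 3 and 6 months the stated reason to re-program is a fall in overall VAS of less than 50% from baseline. Under the conditional rule the settings on file at these visits would come mostly from subjects in whom the therapy worked less well, while the summary would be read as describing all subjects on DTM-LE. Last known settings could be carried forward for the others, but the plan does not say so. Impedance not measured at a visit cannot be recovered.

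A related gap is that each visit records both initial and final settings, and SAP 7.9.2.2 does not say which is summarised. At the 12-Month visit subjects are programmed per standard of care before exit (10.12.4), so the final settings there may no longer describe the study therapy.

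**Working it through.** **1. The plan's own sizing.** With N = 30 and SD 2.6 (protocol 14.8), the half-width is t(0.975, 29) × SD/√N = 2.045 × 2.6/√30 = 0.971, which matches the stated 0.97. Enrolment is 30/(0.90 × 0.60) = 55.6, which matches the stated 56. These figures concern VAS. They are used here only to fix 30 as the planned number at 3 months.

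**2. The two rules by visit.**

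| Visit | Table 10-1, visit list, 10.17.11 | Upload sentence in the visit section | Effect of the conditional wording in the synopsis and 10.14 |
|---|---|---|---|
| 1-Month | required | no condition | in tension, but the visit section is clear |
| 3-Month | required | only if re-programmed | live conflict |
| 6-Month | required | only if re-programmed | live conflict |
| 12-Month | required | no upload sentence | condition met anyway, because subjects are programmed at the end of the visit (10.12.4) |

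The conflict is therefore concentrated at 3 and 6 months.

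**3. Number of subjects under the conditional rule, worst case.** Let q be the share with less than 50% relief at 3 months. The documents give no value, so 20% to 50% is assumed. Assume also that every such subject is re-programmed (the protocol only permits it) and that nothing is captured from anyone else. The number contributing is 30 × q: 30 × 0.20 = 6 and 30 × 0.50 = 15.

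As a yardstick for lost precision only, since no confidence interval is planned for settings, t(0.975, n−1)/√n is 0.37 SD at n = 30, 0.55 SD at n = 15 and 1.05 SD at n = 6.

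**4. Bias.** Let d be the difference in mean setting between subjects below 50% relief and the rest. The full mean is q × (mean below) + (1−q) × (mean of the rest), so using only the first group shifts the result by (1−q) × d. If d = 0 the shift is zero. If d were 0.5 SD (an assumption), the shift would be 0.8 × 0.5 = 0.40 SD at q = 20% and 0.5 × 0.5 = 0.25 SD at q = 50%. Nothing in the documents gives the size or sign of d.

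**5. Whether separate means give energy use.** They do not, because charge per second is a product of the settings. The DTM-LE cycling limits are not visible, so this illustration borrows the range quoted for another therapy in protocol 4.1, read as ON:OFF. One subject at 30 s:90 s has a duty cycle of 30/120 = 25.0%, and one at 30 s:360 s has 30/390 = 7.7%; the mean is 16.3%. Mean ON of 30 s with mean OFF of 225 s implies 30/255 = 11.8%, which is 28% lower. These are the extremes of that range. If all subjects cycle alike, the discrepancy is zero.

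**The case against.** The other side has several good points.

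- **The table governs.** The synopsis refers to the procedure table for visit requirements, and protocol 10.2 does the same. Table 10-1 ticks the interrogation-report row without condition at Trial End, Implant, Activation and every follow-up visit. This stands, and it shows which way to resolve the conflict. It also nearly disposes of the mismatch at Trial End and Implant in the programming-parameter row. It does not remove the contrary sentences at the point where site staff read the visit procedure.
- **The conditional sentences in 10.12.2 and 10.12.3 concern upload, not collection.** That is true of those two, but Section 10.14 also conditions obtaining the reports and impedance, and upload is the described route to the database. The Scheduled Follow Up CRF in SAP 7.10 is cited for checking DTM-LE limits; the SAP does not say it holds the setting or impedance values.
- **Monitoring would catch it.** Protocol 10.20 lists missing required interrogation files as a deviation, and Table 10-1 marks them required. This is a real safeguard, weakened because the passages differ on what is required.
- **The count of 6 to 15 stacks assumptions.** It does, and it is offered only as a worst case. Imaging and unscheduled visits could add records.

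A reader might infer that the secondary population is undefined. The documents do not support that: protocol 14.1.2, SAP 7.4 and SAP 7.9.2.4 all name the Per-protocol set. The synopsis and protocol 14.5.4 are looser, with no programming condition, and need aligning. The formal set definitions are not visible, so no fault in them is claimed.

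**Conclusion.** The inconsistency is real for the 3- and 6-Month visits and should be corrected. If sites follow the conditional text, secondary-endpoint settings and impedance at those visits would come mainly from subjects with less than 50% relief. In the worst case 6 to 15 of 30 subjects would contribute, on the assumptions stated above, and the bias in mean settings is of unknown size and direction. If sites follow Table 10-1, nothing is lost.

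Two stronger readings are not supported. One is that settings will be missing throughout follow-up: the 1-Month section has no condition, and programming at the end of the 12-Month visit satisfies the condition in 10.14. The other is that the lack of a per-subject energy value is an error. Listing settings meets the objective as worded, recharge interval is already named as an optional summary in SAP 7.9.2.3, and most additional objectives are not visible, so an energy measure there cannot be ruled out. A derived charge value would be a useful addition because energy use is part of the stated purpose (protocol 4.2), but the 28% example is not an estimate for this study.

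**What to change.** 1. In the protocol synopsis and Sections 10.12.2, 10.12.3 and 10.14, state that interrogation reports, settings and impedance are obtained and uploaded at every scheduled follow-up visit whether or not re-programming occurs. This agrees with Table 10-1 and 10.17.11. Change footnote f of Table 10-1, which makes impedance optional, to agree with SAP 7.9.2.2, which includes it in the endpoint.
2. In SAP 7.9.2.2, state that follow-up summaries use the initial settings found on arrival, and that Trial Start and Activation use the final settings.
3. Align the synopsis statistics paragraph and protocol 14.5.4 with the Per-protocol set named in protocol 14.1.2, SAP 7.4 and SAP 7.9.2.4.
4. Optionally, add a descriptive charge per second for each subject and visit: amplitude × pulse width × frequency × duty cycle, with duty cycle = ON/(ON + OFF), summed over the programs running, where the report allows it.

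The cost is a protocol amendment with IRB approval (protocol 16.6), one interrogation per scheduled visit where a site would otherwise skip it, and a little more analysis. The charge value will be missing where the report does not identify the group in use.
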